12.2. Peer review

This study has been peer reviewed as part of the British Orthodontic Society Foundation (Funder) application process.

12.3. Public and Patient Involvement

Prior to use, the participant and parent information sheets and questionnaires will be piloted with our orthodontic population to ensure that they are age-appropriate for the patients that may be eligible for the trial. This will include looking at health literacy as well as ease of use and clarity of the instructions given. Feedback from this will be used to make any necessary amendments prior to use in the trial.

12.4. Research Ethics Committee (REC) & Regulatory Considerations

The study will be conducted in compliance with the approved protocol and the Declaration of Helsinki. The protocol and all related documentation (e.g. informed consent form, PIS, questionnaires) have been reviewed and received approval by a Research Ethics Committee (REC). The investigator will not begin any participant activities until approval from the HRA and REC has been obtained and documented. All documentation and correspondence must be retained in the trial master file/investigator site file. Substantial amendments that require HRA and REC (where applicable) review will not be implemented until the HRA and REC grants a favourable opinion (with the exception of those necessary to reduce immediate risk to participants).

It is the responsibility of the CI to ensure that an annual progress report (APR) is submitted to the REC within 30 days of the anniversary date on which the favourable opinion was given, annually until the study is declared ended. The CI is also responsible for notifying the REC of the end of study (see Section 6.9) within 90 days. Within one year of the end of study, the CI will submit a final report with the results, including any publications/abstracts to the REC.

Before any site can enroll a patient into the study confirmation of capacity must be sought from the site's research and development (R&D) department. In addition, for any amendment that will potentially affect the site's permission, the research team must confirm with the site's R&D department that permission is ongoing (Section 11.10).

12.5. Protocol Compliance / Non-compliance Reporting

The investigator is responsible for ensuring that the study is conducted in accordance with the procedures described in this protocol. Prospective, planned deviations and/or waivers to the protocol are not acceptable, however accidental protocol deviations (non-compliances) may happen and as such these must be recorded. Non-compliances should be recorded in the CRF and/or a non-compliance log kept in the ISF. All non-compliances should be reviewed and assessed by the PI (or appropriately delegated individual) to determine if they meet the criteria of a "serious breach" (Section 12.6). Non-compliances which are found to frequently recur are not acceptable, will require immediate action, and could potentially be classified as a serious breach.

12.6. Notification of Serious Breaches to GCP and/or the Protocol

A "serious breach" is a departure from the protocol, Sponsor procedures (i.e. SOPs), or regulatory requirements which is likely to effect to a significant degree –

- (a) The safety or physical or mental integrity of the subjects of the study; or
- (b) The scientific value of the study.

If the PI (or delegate) is unsure if a non-compliance meets these criteria, they should consult the Sponsor for further guidance.

If a serious breach is identified the investigator should notify the Sponsor immediately (i.e. within 1 working day) using the 'Non-CTIMP Notification of a Serious Breach' form. The report will be reviewed by the Sponsor and CI, and where appropriate, the Sponsor will notify the REC within 7 calendar days of being made aware of the breach.

12.7. Data Protection and Patient Confidentiality

The study will be conducted in accordance with the Data Protection Act 2018. The investigator must ensure that participant's anonymity is maintained throughout the study and following completion of the study. Participants will be identified on all study specific documents (except for the informed consent form and enrolment log) only by the participants study specific identifier (and initials if deemed necessary). This identifier will be recorded on documents, biological samples and the database. The Investigator Site File will hold an enrolment log detailing the study specific identifier alongside the names of all participants enrolled in the study.

All documents will be stored securely with access restricted to study staff and authorised personnel.

The CI ([name]) will act as the custodian of the data generated in the study.

12.8. Financial and Other Competing Interests for the Chief Investigator, Principal Investigators at Each Site and Committee Members for the Overall Study Management

There are no conflicts of interest that could influence study design, conduct or reporting to declare.

12.9. Indemnity

As UHDB is acting as the research Sponsor for this study, NHS indemnity applies. NHS indemnity provides cover for legal liabilities where the NHS has a duty of care. Non-negligent harm is not covered by the NHS indemnity scheme. UHDB, therefore, cannot agree in advance to pay compensation in these circumstances. In exceptional circumstances an ex-gratia payment may be offered.

12.10. Amendments

If changes to the study are required these must be discussed with the Sponsor, who is responsible for deciding if an amendment is required and if it should be deemed substantial or non-substantial. Substantial amendments will be submitted to the relevant regulatory bodies (REC, HRA) for review and approval. The amendments will only be implemented after approval and a favourable opinion has been obtained. Non-substantial amendments will be submitted to the HRA for their approval/ acknowledgment. Amendments will not be implemented until all relevant approvals are in place.

13. DISSEMINATION POLICY

13.1. Dissemination Policy

Intellectual property arising from the study will remain ownership of the University Hospitals of Derby and Burton NHS Foundation Trust. On completion of the study, the data will be analysed and tabulated. This will feed into a Final Study Report. It is anticipated that the results of the study will be published by the research team in an appropriate peer-reviewed journal. The funders request

Orthodontic Patient Experience of Intraoral Scanners Versus Alginate Impressions in the UK: a Single-Centre Randomised Controlled Crossover Trial – UHDB/2021/022 – v2.0 – 20/02/2022

that the information is placed within the public domain within 6 months. In line with funding terms and conditions, the final report will be submitted to the BOSF and published on their webpages. Additionally, it is expected that the study will be presented at the British Orthodontic Conference and the aim is for publication in the Journal of Orthodontics or the most relevant journal. In all publications and presentations, the BOSF and the Derby Pump Priming Grant Charitable Funds will be appropriately acknowledged.

Participants will be able to request results of the study following publication of the results and contact details have been provided within the participant/parent information leaflet.

13.2. Authorship Eligibility Guidelines and any Intended Use of Professional Writers

It is expected that any first drafts of publications for academic journals and the final study report will first be authored by the TMG as per the named CI and co-applicants. Final authorship shall be in accordance with the International Committee of Journal Medical Editors (ICJME) guidance (International Committee of Medical Journal Editors 2019).

15. APPENDICES

15.1. Appendix 1 – Schedule of Assessments

| Procedures | Visits | | |
|---|--------------|--------------------|--------------|
| | 1. Screening | 2. Treatment phase | 3. Follow up |
| Informed consent | X | X | |
| Demographics | | X | |
| Medical history | X | X | X |
| Dental health education | X | | |
| Eligibility assessment | X | | |
| Randomisation | | X | |
| New patient examination (if necessary) | | X | |
| Orthodontic treatment consent | | X | X |
| Compliance | | | |
| Assessment 1 (Alginate impression) | | X | X |
| Assessment 2 (Intraoral scan) | | X | X |
| Orthodontic treatment including appliance fit | | | X |
| Adverse event assessments | | X | X |
| Physician's Withdrawal Checklist | X | X | X |

15.2. Appendix 2 – Amendment History

| Amendment No. | Protocol version no. | Date issued | Author(s) of changes | Details of changes made |
|---------------|----------------------|-------------|----------------------|---|
| 1 | 2.0 | 20/02/2022 | [name] | 
Removal of reference to Gillick competence and individuals with parental consent rights
 
Added reference to the assent form
 
Update version number and dates
 
Added NCT number
 
Minor formatting/spelling amendments
 |

[F.1] Definition of Analysis Groups [Protocol Sec. 10.7].....	5
[F.2] Definition of Inclusion Groups	6
[F.3] Procedure for Accounting for Missing, Unused, and Spurious Data [Protocol Sec. 10.8]	6
[G] COMMENTS	6
APPENDIX A. DUMMY TABLES.....	7
APPENDIX B. CONSORT DIAGRAM	9

[A] Sample Size

[A.1] Sample Size Estimation / Power Calculation [Protocol Sec. 10.1]

[A.1.1] The sample size calculations are recorded in “Dentalscans Sample Size Verification_v1 25Jun2021.pdf” in the eTMF and summarised in the protocol.

[A.2] Sample Size Amendments After Interim Analysis

[A.2.1] Not applicable – there will be no interim analysis

[A.3] Final Sample Size

[A.3.1] Not applicable

[B] Randomisation [Protocol Sec. 7.3]

[B.1.1] Full details of the randomisation are recorded in the randomisation specification “OPESI Randomisation Specification_TRUNCATED_v1.0_13APR2022” in the eTMF and summarised in the protocol.

[C] Interim Analysis [Protocol Sec. 10.6]

[C.1.1] There will be no interim analyses.

[D] Justification for Interim Analysis

[D.1] Definition of Endpoints used in Interim Analysis

[D.1.1] Not applicable

[D.2] Statistical Methods for Interim Analysis

[D.2.1] Not applicable

[E] Final Statistical Analysis [Protocol Sec. 10.3]

[E.1] Summary of Baseline Data [Protocol Sec. 10.3.1]

[E.1.1] Descriptive statistics will be presented to summarise the distribution of baseline variables (age and gender) across each of the randomisation groups. Age will be reported with means & 95% confidence intervals (95% CI), if shown to be normally distributed, using a combined skewness and kurtosis test, otherwise will be reported with medians & Interquartile Ranges (IQR). Gender will be reported with frequencies & percentages.

[E.1.2] A Consolidated Standards of Reporting Trials (CONSORT) flow diagram will be produced, showing the frequency of patients / participants;

- Assessed for eligibility (screening),
- Found eligible,
- Reasons for not consenting,
- Given consent,
- Excluded before randomisation (and the frequency of each reason for withdrawing consent),
- Randomised,
- Allocated to each randomisation group,
- That received each allocated intervention,

- That did not receive each allocated intervention,
- Lost to follow-up (and the frequency of each reason for loss to follow-up) for each randomisation group,
- Analysed for each randomisation group,
- Not analysed (and the frequency of each reason for not being analysed) for each randomisation group.

[E.2] Definition of Primary Endpoint [Protocol Sec. 10.3.2]

[E.2.1] The primary endpoint is the difference between two (identical) visual analogue scales (VAS), both completed by the patient, measuring the comfort of each procedure. One VAS will measure the comfort of the impression and the other VAS will measure the comfort of the scan. Each VAS will be measured by two operators and a mean of their measurements will be recorded for each scale. The difference between each participant's mean comfort VAS scores for the two procedures will be calculated.

[E.3] Statistical Methods for Primary Analysis [Protocol Sec. 10.3.2]

[E.3.1] The mean of the differences between procedures will be reported for each treatment sequence with 95% confidence intervals. The difference between the paired VAS will be compared using analysis of variance (ANOVA) that will analyse the period, treatment and sequence effects of the comfort scores. Analysis of the primary endpoint will be assessed using 2-sided tests with a significance level of 0.05.

[E.4] Definition of Secondary Endpoints [Protocol Sec. 10.3.2]

[E.4.1] Patients will complete 4 secondary endpoints, each of which will be measured using two (identical) VAS, both completed by the patient, to measure four different features of each procedure (see section E.4.2 for details of the features the patients will assess). For each assessment, a VAS will be scored for the impression and another for the scan. Each VAS will be measured by two operators and a mean of their measurements will be recorded for each VAS.

[E.4.2] The patients will assess

1. pain
2. the speed of the procedure,
3. nausea and / or coughing
4. to what degree the patient would recommend the procedure

[E.4.3] Orthodontic operators will complete 4 secondary endpoints, each of which will be measured using two (identical) VAS, both completed by the operator, to measure four different features of each procedure (see section E.4.4 for details of the features the operators will assess). For each assessment, one VAS will be a measurement of the impression and the other will measure the scan. Each completed VAS will be measured by two operators (using rulers) and a mean of their measurements will be recorded for each scale.

[E.4.4] The operators will assess

1. Ease of impression
2. Confidence taking the impression
3. Relative speed of the impression
4. whether the patient felt sick or coughed during the procedure

[E.4.5] The time taken to make the impression or complete the scan will be recorded (mins)

[E.4.6] A secondary analysis of the primary outcome will be undertaken using a two-period two-treatment mixed effects model.

[E.4.7] If some participants have not complied with the protocol, a second analysis of the primary outcome will be conducted just including participants that were compliant.

[E.5] Statistical Methods for Secondary Analyses [Protocol Sec. 10.3.2]

[E.5.1] Eight of the secondary outcomes will be recoded using VAS scores (see Sections E.4.2 and E.4.4). The differences between the paired VAS scores of these secondary outcomes will be reported using means and 95% confidence intervals. They will be compared using analysis of variance (ANOVA) that will analyse the period, treatment and sequence effects of the comfort scores. Analysis of the secondary endpoint will be assessed using 2-sided tests with a significance level of 0.05.

[E.5.2] The mean difference in the time required for each procedure (Section E.4.5) will be reported, with 95% confidence intervals. The difference in time will be compared using analysis of variance (ANOVA) that will analyse the period, treatment and sequence effects of the comfort scores. Analysis of the secondary endpoint will be assessed using 2-sided tests with a significance level of 0.05.

[E.5.3] The operator's preference for each impression (Section E.4.6) will be tabulated and reported using frequencies and percentages.

[E.5.4] The secondary analysis of the primary outcome using a two-period two-treatment mixed effects model (Section E.4.7) will be undertaken with participant effects treated as random and a treatment-by-period interaction (for this analysis, the carryover effect) included in the model. The mean effects will be reported, with 95% confidence intervals.

[E.5.5] The potential second analysis of the primary outcome (Section E.4.8) will be a per protocol analysis of the difference between the paired VAS. This will be carried out using an analysis of variance (ANOVA) that will analyse the period, treatment and sequence effects of the comfort scores. Analysis of the primary endpoint will be assessed using 2-sided tests with a significance level of 0.05. The mean effects of this model will be reported, with 95% confidence interval

[E.6] Statistical Methods for Sub-group Analyses [Protocol Sec. 10.4]

[E.6.1] There will be no sub-group analyses

[E.7] Statistical Methods for Sensitivity Analyses [Protocol Sec. 10.3.2]

[E.7.1] If there are missing data in the primary endpoint, the plausibility that outcome data are missing at random (MAR) from the primary endpoint will be examined, and if it doesn't hold, sensitivity analysis will be conducted. Otherwise, sensitivity analyses will not be undertaken.

[E.8] Definition of Safety Endpoints [Protocol Sec. 8]

[E.8.1] The safety endpoints will be the reported SAEs and SUSARs.

[E.9] Statistical Methods for Safety Endpoints

[E.9.1] The number and percentage of patients reporting a SAE or SUSAR will be summarised by treatment group and compared using a Chi-Square test.

[F] Analysis Groups and Missing Data

[F.1] Definition of Analysis Groups [Protocol Sec. 10.7]

[F.1.1] **Modified Per Protocol:** All participants who were randomised and experienced at least one of the study treatments will be included in the primary analysis. Participants will be

analysed according to the treatment sequence they received, if this differs from the treatment sequence to which they were allocated.

The safety data will be reported for all participants who experienced at least one of the study treatments. They will be reported according to the treatment they received at the time of experiencing the SAE or SUSAR, or the most recent treatment if the event occurred after the method was administered.

[F.1.2] Per protocol: If required, the secondary analysis will be carried out on patients who experienced both procedures. They will be analysed according to the treatment sequence they received if this differs from the treatment sequence to which they were allocated.

[F.2] Definition of Inclusion Groups

[F.2.1] Complete Dataset Population: Missing data are expected to be small and the primary analysis is planned to be carried out on a complete case basis. For the secondary analyses, any participant who has incomplete data will be excluded from the analysis that requires those data.

[F.3] Procedure for Accounting for Missing, Unused, and Spurious Data [Protocol Sec. 10.8]

[F.3.1] If there are missing data in the primary endpoint, then multiple imputation using chained equations will be applied. Missing data will not be imputed for any of the secondary endpoints, which will be analysed on a complete case basis.

[G] Comments

[G.1.1] The analyses will be carried out using STATA.

[G.1.2] The protocol describes another secondary outcome, which is the operator's preference for scans or impressions. This will be analysed qualitatively and is therefore outside the scope of this analysis plan.

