10.3.2. Outcome Analysis

The primary outcome

The primary endpoint is the difference between two (identical) visual analogue scales (VAS) measuring the comfort of each procedure. One VAS will measure the comfort of the impression and the other VAS will measure the comfort of the scan. Each VAS will be measured by two operators and a mean of their measurements will be recorded for each scale. The difference between each participant's mean comfort VAS scores will be calculated. The mean of the differences will be reported for each treatment sequence with 95% confidence intervals.

The difference between the paired VAS will be compared using analysis of variance (ANOVA) that will analyse the period, treatment and sequence effects of the comfort scores. Analysis of the primary endpoint will be assessed using 2-sided 0.05 levels, consistent with the type I alpha level used in the trial design.

The secondary outcomes

- Four modified 100mm VA scales to measure the participant's experiences of:
 - Pain;
 - Relative speed of impression;
 - Nausea and/or coughing;
 - Whether the impression method could be recommended; and
- Four 100mm VA scales to measure the orthodontic operator's experience of:
 - Ease of impression;
 - Confidence taking the impression;
 - Relative speed of impression; and
 - Whether the participant felt sick or coughed during the procedure.
- The time taken to make the impression or complete the scan will be recorded (mins)
- A simple question to determine operator preference for intraoral scanning versus alginate impressions.

The 8 secondary outcomes measured by VAS and the time taken to make the impression or complete the scan will be compared using analyses of variance suitable for a crossover study, that will test the period, treatment and sequence effects on these nine secondary outcomes. The mean differences between the paired VAS scores (e.g., Pain from scan and pain from impression) will be reported with 95% confidence intervals.

The operator's preference will be reported using descriptive statistics. The frequency and percentages will be recorded.

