In addition, two secondary analyses of the primary outcome may be undertaken. The first analysis will be conducted and will use a two-period two-treatment mixed effects model: Participant effects will be treated as random and a treatment-by-period interaction (for this analysis, this is the carryover effect) will be included in the model. If some participants have not complied with the protocol, a second analysis of the primary outcome will be conducted just including participants that were compliant (i.e.

a per protocol analysis). For both of these analyses, the mean effects will be reported, with 95% confidence intervals.

Only the primary analysis will be compared against a specific level of significance. The secondary analyses should be considered as hypothesis generating rather than providing firm conclusions.

The analysis will be undertaken by the study statistician. The study statistician will draft the Statistical Analysis Plan (SAP) according to CTU-SOP-019 (Statistical Analysis Plan), which will be reviewed by the CI and approved by the CI and the study statistician. The analysis will be carried out using STATA® and a statistical report produced.

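### Does the plan leave the primary comfort outcome without an overall treatment estimate and confidence interval?

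*SAP*

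**What the plan says.** On the primary outcome the two documents match. SAP E.3.1: "The mean of the differences between procedures will be reported for each treatment sequence with 95% confidence intervals". Protocol 10.3.2: "The mean of the differences will be reported for each treatment sequence with 95% confidence intervals". Both then specify an ANOVA of period, treatment and sequence effects, and both set a two-sided 0.05 level for the primary endpoint.

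Secondary outcomes are worded without the split by sequence. Protocol 10.3.2: "The mean differences between the paired VAS scores (e.g., Pain from scan and pain from impression) will be reported with 95% confidence intervals". SAP E.5.1: "The differences between the paired VAS scores of these secondary outcomes will be reported using means and 95% confidence intervals". SAP E.5.2: "The mean difference in the time required for each procedure (Section E.4.5) will be reported, with 95% confidence intervals".

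The mixed model in SAP E.5.4 has random participant effects and "a treatment-by-period interaction (for this analysis, the carryover effect) included in the model". Its output is described as follows: "The mean effects will be reported, with 95% confidence intervals". The protocol's counterpart, which also covers the per-protocol rerun, reads: "For both of these analyses, the mean effects will be reported, with 95% confidence intervals". SAP E.5.5 uses similar words for the per-protocol ANOVA.

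SAP Appendix A has a primary-analysis table for a continuous endpoint. It has one column per treatment, a column for the difference between treatments laid out as an estimate with an interval, and a p-value. The table is still a template: treatments are X and Y, a categorical primary endpoint is also shown, and the section reference is D.3.1 although the primary analysis is in E.3.1.

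**The concern.** In a two-period crossover the two sequence means are not two estimates of the same thing. Each is the treatment effect shifted by the period effect, in opposite directions, and each uses half of the participants. If they were the only intervals reported, a reader would have nothing that corresponds to the primary test, and nothing to set directly against the 11 mm difference in Protocol 10.1. It also looks odd that the narrative is more explicit about an overall difference for pain or procedure time than for comfort.

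The mixed model raises a related question. Once a treatment-by-period term is in the model, the coefficient labelled treatment depends on the coding. With reference coding it is the period-1 comparison between participants; with centred coding it is the within-participant effect averaged over the periods. An undefined mean effect could be either. At stake is which number is printed, not which hypothesis is tested.

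**Working it through.** **1. What the trial is powered for.** Inputs from Protocol 10.1: alpha 0.05, power 0.9, difference 11 mm, SD 29.85 mm; SAP E.3.1 gives two-sided testing.

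- N = (29.85 × (1.960 + 1.282) / 11)² = 77.4, so 78 in total, or 39 per sequence.
- 39 / (1 − 0.07) = 41.9, so 42 per sequence and 84 in total.

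Both stated figures are reproduced. The protocol does not say what the SD describes. The calculation works with 29.85 as the SD of paired differences (or as a single-score SD with correlation 0.5, which gives the same SD of differences). The design is therefore sized for the overall paired difference.

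**2. Which contrast the ANOVA gives.** Let D be scan minus impression, τ the treatment effect and π the period-2 minus period-1 effect, with no carryover.

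- Impression first: mean of D = τ + π.
- Scan first: mean of D = τ − π.
- Average of the two = τ.

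With period, treatment and sequence in the model and complete data, the treatment effect is this average. For an assumed π of 5 mm and τ of 11 mm, the sequence means centre on 16 and 6 mm, and their average is 11 mm.

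**3. Whether the promised outputs are enough.** At 39 per sequence:

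| Quantity | SE (mm) | 95% CI half-width (mm) |
|---|---|---|
| One sequence mean | 29.85/√39 = 4.78 | 9.7 (t, 38 df) |
| Overall difference | 29.85/√78 = 3.38 | 6.7 (t, 76 df) |

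Combining the two sequence results gives √(4.78² + 4.78²)/2 = 3.38 mm, the overall SE. The promised means and intervals therefore yield the overall estimate and its precision.

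**4. Room for a rival primary estimate.** The only other natural figure is the plain mean of all paired differences. It departs from the average of sequence means by π(n1 − n2)/N. With an assumed 42 and 36 completers:

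- π = 5 mm: 5 × 6/78 = 0.4 mm.
- π = 10 mm: 10 × 6/78 = 0.8 mm.

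Both are small beside a 6.7 mm half-width, and the plan's ANOVA already removes the period effect.

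**5. The mixed model.** If ρ is the correlation between a participant's two scores, the single-score SD is s = 29.85/√(2(1 − ρ)) and the period-1 contrast has SE = s√(2/39).

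| Assumed ρ | s (mm) | Period-1 SE (mm) | Averaged-effect SE (mm) |
|---|---|---|---|
| 0 | 21.11 | 4.78 | 3.38 |
| 0.25 | 24.37 | 5.52 | 3.38 |
| 0.5 | 29.85 | 6.76 | 3.38 |

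One simulated data set (39 per sequence, true effect 11 mm, period effect 5 mm) shows the same: 8.17 mm (SE 6.00) under reference coding and 10.89 mm (SE 3.09) under centred coding. The latter equals the average of its sequence means, (12.67 + 9.11)/2 = 10.89. The ambiguity is real but confined to how this one analysis is labelled.

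**The case for a change.** The best case for a change is that it costs a sentence in each place and fixes, before data are seen, which number is read against 11 mm. An ANOVA table on its own gives tests, not intervals. The Appendix A table is an unadapted template and does not say whether the difference is period-adjusted. A reader given only the sequence intervals could also see apparent conflict with the test: for a true 11 mm difference and no period effect, one sequence interval excludes zero in about 61% of trials and both in 0.611² = 37%, against 89.5% for the overall test.

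Some of this stands. The narrative is less explicit than it could be, and the D.3.1 reference is a clerical slip. The percentages do not carry weight, because nowhere does the plan draw an inference from the sequence intervals; the 0.05 test belongs to the primary endpoint analysis. The template, generic as it is, does ask for the treatment difference with an interval. SAP E.5.5 expects effects with intervals from the per-protocol run of the same ANOVA, which suggests how the authors intend that model to be reported. For the mixed model, a mean effect most naturally denotes the effect averaged over periods, and a crossover statistician would be unlikely to report a period-1 comparison under that name.

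**Conclusion.** The wording is incomplete, but the plan is not silent and no change is needed. The overall difference is fixed by the ANOVA that the plan specifies, has a place in Appendix A, and can be recovered from the results promised by sequence. At 78 completers its 95% CI half-width is about 6.7 mm, and t-based power for 11 mm is 89.5%. Spelling out the contrast alters neither these figures nor the test or the sample size. The only identified alternative for the primary estimate moves it by 0.4 to 0.8 mm under the assumed imbalance and period effects.

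The mixed-model ambiguity is larger in standard-error terms (4.78 to 6.76 mm against 3.38 mm for ρ from 0 to 0.5). It concerns an analysis that Protocol 10.3.2 treats as exploratory and for which SAP E.5.4 sets no significance level. On complete data its averaged effect repeats the primary estimate.

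These figures assume 29.85 mm is the SD of paired differences, 39 completers per sequence and complete data. The period effects, the completer imbalance and ρ are assumptions; the documents give none of them.

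### The SAP sets a two-sided 0.05 level for nine secondary outcomes and the per-protocol re-analysis, although the protocol reserves a significance level for the primary analysis

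*SAP*

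**What the plan says.** Protocol 10.3.2 sets a two-sided 0.05 level for the primary endpoint, then limits it: "Only the primary analysis will be compared against a specific level of significance". The next sentence reads: "The secondary analyses should be considered as hypothesis generating rather than providing firm conclusions". For the two further analyses of comfort, the mixed model and the per-protocol analysis, the protocol asks for estimation only: "For both of these analyses, the mean effects will be reported, with 95% confidence intervals". It does plan ANOVAs for the eight secondary VAS scales and procedure time "that will test the period, treatment and sequence effects on these nine secondary outcomes", but gives no level for them.

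The SAP differs in three places:

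- **E.5.1** (eight VAS outcomes) and **E.5.2** (time) each state: "Analysis of the secondary endpoint will be assessed using 2-sided tests with a significance level of 0.05".
- **E.5.5** (per-protocol re-analysis of comfort, done only if some participants did not comply) states: "Analysis of the primary endpoint will be assessed using 2-sided tests with a significance level of 0.05".

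E.5.4, on the mixed model, gives no level: "The mean effects will be reported, with 95% confidence intervals".

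**The concern.** The SAP's section E.5 cites Protocol 10.3.2 as its source, yet it applies a decision threshold that the protocol reserves for the primary analysis. An analyst who follows the SAP would declare significance, or its absence, for pain, nausea or coughing, speed, recommendation, the operator ratings and time. Where compliance is imperfect, there would also be a second 0.05 verdict on comfort, which could disagree with the primary one.

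What is at stake is what the trial may claim on its secondary outcomes. With two governing documents in conflict, a report could present an unadjusted p<0.05 as a finding and cite the SAP for it, while the protocol calls the same result hypothesis generating.

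**Working it through.** **1. Where each document applies a significance level**

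| Analysis | Protocol 10.3.2 | SAP |
|---|---|---|
| Primary: comfort, ANOVA | two-sided 0.05 | two-sided 0.05 (E.3.1) |
| Eight secondary VAS outcomes | tested, no level | two-sided 0.05 (E.5.1) |
| Procedure time | tested, no level | two-sided 0.05 (E.5.2) |
| Mixed model for comfort | mean effects, 95% CI | mean effects, 95% CI (E.5.4) |
| Per-protocol re-analysis of comfort | mean effects, 95% CI | two-sided 0.05, plus mean effects and 95% CI (E.5.5) |

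The documents agree on the first and fourth rows and conflict on the other three. The SAP is also inconsistent within E.5: the protocol treats the mixed model and the per-protocol analysis alike, and the SAP does not. Its Comments section notes one scope difference from the protocol (operator preference) but not this one.

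**2. The plan's own figure**

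Neither document gives an overall error rate for the secondary outcomes. The only design figure tied to a level is the sample size in Protocol 10.1: two-sided alpha 0.05, power 0.9, SD 29.85, difference 11 mm. Taking 29.85 as the SD of the paired difference, which the protocol does not state:

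N = (29.85 × (1.960 + 1.282) / 11)² = 77.4, rounded up to 78, or 39 per sequence.

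Allowing for 7% dropout, 39 / 0.93 = 41.9, rounded up to 42 per sequence and 84 in total. This matches the protocol. The calculation covers one test, the primary, so removing a level from the secondary outcomes changes nothing here.

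**3. Chance of at least one false positive over the nine treatment comparisons**

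Inputs: k = 9 (eight VAS outcomes plus time), each at two-sided 0.05, with all nine null hypotheses true.

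- Independent tests: 1 − 0.95⁹ = 1 − 0.630 = 0.370.
- Bound under any dependence: 9 × 0.05 = 0.45, which is also the expected number of false positives.
- Common correlation ρ between normal test statistics: 1 − ∫ φ(g) [Φ((1.96 − √ρ·g)/√(1−ρ)) − Φ((−1.96 − √ρ·g)/√(1−ρ))]⁹ dg.

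| Assumed ρ | Numerical integration | Simulated crossover t-tests (39 per sequence, 76 df, 40,000 runs) |
|---|---|---|
| 0 | 0.370 | 0.370 |
| 0.3 | 0.326 | 0.326 |
| 0.5 | 0.269 | 0.275 |
| 0.7 | 0.202 | 0.206 |

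Some outcomes overlap by construction: patient-rated speed, operator-rated speed and measured time; and patient- and operator-rated nausea or coughing. With an assumed 0.7 within these two clusters and 0.3 between all other pairs, simulation (400,000 draws) gives about 0.30.

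**4. The per-protocol re-analysis**

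Counted as a tenth independent test it would give 1 − 0.95¹⁰ = 0.401. That overstates its contribution: it uses the primary outcome and largely the same participants, so it is close to a repeat of the primary test. It is therefore left out of the figures above. The problem with E.5.5 is a second verdict on comfort, not added independent error.

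**5. A related drafting slip**

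E.5.1 and E.5.2 describe the ANOVA effects as effects of the comfort scores, apparently carried over from E.3.1. The protocol refers to effects "that will test the period, treatment and sequence effects on these nine secondary outcomes". The 0.05 sentence may have been carried over in the same way.

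**The case against.** The strongest reply is that the conflict has little practical effect. The SAP already reports 95% confidence intervals for all these outcomes, and nine unadjusted intervals have the same chance that at least one excludes zero. The protocol itself plans to test the nine outcomes, and the E.5 heading points to the protocol section that contains the hypothesis-generating statement. That statement follows a paragraph on the two further analyses of comfort, so it could be read as covering only those two. Protocol 10.7 describes the per-protocol analysis as a re-analysis of the primary analysis, which makes it understandable that its level was carried over. Finally, the 37% assumes that all nine nulls are true, although some studies cited in the background report time differences, and every correlation used is assumed.

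Much of this is fair and limits the weight of the point. The dispute is about the threshold, not about fitting ANOVAs, and the error figures illustrate the risk without establishing the conflict. But none of it reconciles the two documents:

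- The sentence reserving a significance level for the primary analysis excludes the nine outcomes even if the hypothesis-generating sentence is read narrowly.
- The per-protocol analysis is one of the two analyses covered under that narrow reading, so E.5.5 conflicts either way.
- A cross-reference in a heading does not cancel an explicit 0.05 rule in the text below it.

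**Conclusion.** The concern holds. SAP E.5.1, E.5.2 and E.5.5 apply an unadjusted two-sided 0.05 level where Protocol 10.3.2 applies none. This can be seen from the texts and rests on no assumption. It should be fixed before analysis, because it decides whether secondary results may be called significant.

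If p<0.05 were treated as a finding, the risk of at least one false secondary claim would be about 20% to 37% over the correlations considered, and about 30% in the clustered case. The 37% is the ceiling for jointly normal test statistics with all nine nulls true. The documents give no correlations, so the lower figures depend on assumed values.

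The type I error, estimate and sample size of the primary analysis are unaffected. Removing the threshold does not lower the underlying error rate; it restores the protocol's limit on how the results may be read.

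**What to change.** In the SAP:

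1. Delete the sentence setting the 0.05 level from E.5.1, E.5.2 and E.5.5. The mean differences or effects with 95% confidence intervals are already specified there and stay.
2. Add to E.5: *All secondary analyses are hypothesis generating; no significance level is applied, and a 95% confidence interval that excludes zero is not a confirmatory finding.* If p-values from the planned ANOVAs are shown, give them without a threshold.
3. In E.5.1 and E.5.2, replace the reference to comfort scores with the outcome being analysed.

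This costs SAP wording only, with no new data, no new analyses and no protocol amendment. The price is that secondary claims become weaker, as the protocol intends.

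If the sponsor wants confirmatory secondary claims, prespecify a procedure such as Holm over the nine treatment comparisons (smallest p-value against 0.05 / 9 = 0.0056) and amend Protocol 10.3.2 to match. That route needs a protocol amendment.
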